The study was powered to address aim 1, the impact of the intervention on non-fatal overdose. For the study of each opioid user type (heroin and pharmaceutical opioids) the number of subjects needed in each arm of the study (intervention and comparison) to achieve power of 0.80 to detect a decline in the overdose rate from 20% to 10% at a confidence level of 0.05, is 219 subjects. To increase power somewhat and account for potential loss to follow up, we plan to enroll more subjects, 250 in each arm of each study, for a total of 500 heroin using subjects and 500 pharmaceutical opioid, non-heroin using subjects. Other outcomes to be analyzed include drug use and services utilization. Data on brief interventions in ED's shows declines in drug use and ED utilization of at least 40%. Specifically in Washington State, the Screening and Brief Intervention Referral and Treatment (SBIRT) found a 45% reduction in average days of drug use among high risk heroin users who received a brief intervention in an ED (from 15.8 days to 8.7 days in the prior month) and 41% reduction among high risk pharmaceutical opioid users (12.8 to 7.5 days).

Assumptions behind the power estimate are based upon an annual rate of non-fatal heroin overdose estimated to be a median of 25% across studies and for fatal overdoses approximately 1%. For the purposes of this sample size estimate we are conservatively assuming a total annual overdose rate for heroin users of 20%. We believe that a reduction of the OD rate by 50% may be possible based on the potential for additive effects of the OOPEN and the BBCC interventions. Preliminary data on overdose rates for pharmaceutical opioid

abusers (no regular heroin use) indicates a rate approximately half that of heroin users based upon analyses conducted by [name] of interviews from 1,661 clients entering methadone maintenance treatment which indicate a *lifetime* overdose rate for pharmaceutical opioid abusers (25%) that is half the rate of heroin abusers (49%). These findings were extrapolated to a 50% lower rate of *annual* overdose, the validity of which cannot currently be determined, but will be ascertained at the conclusion of this proposed study. We are assuming an annual overdose rate of 10% for pharmaceutical opioid users, or 20% over two years which is the amount of time over which follow up via administrative data will be collected. The power estimates above therefore address one year overdose rates for heroin and 2 years for pharmaceutical opioid users.

Planned methodology

Intent to treat analyses will be the primary analytic approach used to analyze the data resulting from this randomized controlled study. Intent to treat analyses compare those assigned to the intervention group to those in the standard care group, regardless of whether those in the standard care group receive some amount of the intervention.

Planned analyses

Aim 1 Test whether the intervention group has lower rates of opioid overdose and longer time to occurrence of overdose. Overdose will be ascertained at 12 months via self-report and across at least 24 months via administrative data. Because randomized controlled studies are designed to account for potential confounding factors by distributing confounders, measured and unmeasured, equally across comparison and intervention groups, the initial unadjusted analysis will be a logistic regression analysis comparing the probability of opioid overdose in the two study arms. To examine differences in the time to overdose and to account for time varying covariates, such as overdose risk factors, survival analyses will be conducted with the outcome time to overdose(s). A Cox proportional hazards model will be used to investigate the possible association between these factors and event time. We will use sandwich standard error estimates in all statistical tests. Multivariable logistic regression analyses will be conducted to examine the association between predictors and moderators and of the odds of overdose occurrence. Predictors will include treatment assignment and overdose risk factors such as concomitant drug use, interruption in tolerance and homelessness. Potential effect modification will be assessed by including interaction terms for the treatment assignment by severity of opioid and other substance use as measured by the ASSIST. For the pharmaceutical opioid only group, effect modification by opioid user type will be assessed; opioid user typologies will be based upon which inclusion criteria subjects met.

Aim 2 Test whether the intervention group has fewer overdose risk behaviors. These are measured as both binary and continuous data. Binary data will be examined with logistic

regression and continuous data analyzed with ordinary least-squares regression. Analyses will adjust for the overdose risk behavior level or frequency reported at baseline as a concomitant variable, the outcome is the overdose risk behavior at 12 months, and the primary predictor is the treatment group assignment. We will compute robust standard error estimates for each model and use them in all hypothesis tests and confidence intervals.

Aims 3 and 4 Test whether the intervention group has more appropriate health care utilization and lower total health care costs. We will analyze utilization for three separate outcomes: ED visits, outpatient visits, and inpatient hospital admissions as we would expect the intervention to result in declines in ED and inpatient care with concomitant increases in outpatient care over time as patients stabilize their health status. For these analyses we will use a rate modeling approach (negative binomial or Poisson regression, with an exposure adjustment should there be a need to account for differing amounts of follow-up time). We will examine health care costs (combined hospital and ambulance costs) from the health care system perspective.

Mean-per-month health care costs will be calculated for both pre- and post-randomization periods for each individual. We will assess the difference in health care costs across the two study arms by regressing post-randomization mean health care costs on study arm, and controlling for pre-randomization mean health care costs (which should reduce variance and increase power) along with other important covariates. We expect that 500 per arm will be an adequate number to support the use of Ordinary Least-Squares (OLS) regression to model mean cost differences, but will use Generalized Linear Models (GLM) models to examine the sensitivity of OLS results. In addition, we will calculate unadjusted and adjusted cost offsets by adding the cost of the intervention to health care costs and comparing average monthly total costs of services for the intervention group to the average for the standard care group.

Aim 5 Test whether the intervention group has fewer HIV risk behaviors. These are measured as both binary and continuous data. Binary data will be examined with logistic regression and continuous data analyzed with ordinary least-squares regression.

Other analyses

In order to determine whether there is recruitment reactivity, whether those enrolled in either arm of the study have a change in behaviors compared to those not enrolled, we will examine ED re-visit rates at two years for those receiving standard care compared to those with similar demographic characteristics, CPT codes and ED visit dates, but were not enrolled. While this will not directly measure the impact of recruitment on overdose, it will provide some information about recruitment reactivity. Subsequent to intent to treat analyses we will examine whether any subjects in the standard care group received take-home naloxone and overdose prevention and intervention training i.e. “crossed over”. If so, it is possible that this intermediate group might be more similar to the intervention than the standard care group. Crossovers will be identified by an interview question, such as “Did you possess or have ready access to naloxone during the past 3/6 months?” If there is a group that crossed over, post-hoc analyses will compare overdose rates at two years for the cross over group compared to each of the other two study arms. Completion level of administrative data will be assessed by the interview questions at each follow up that document what types of services, in broad categories, were

obtained at non-HMC or non-UWMC facilities or ambulance services not in Seattle-King County. This will allow for an evaluation of *ascertainment bias*, that is, how complete data based on HMC/UWMC and King County ambulance data are and whether there are differential levels of data completion by study arm assignment.

Missing data and dropouts

Missing data will be minimized by the study procedures described above. However, missing data are inevitable and could lead to biased results. Baseline data values and study arm assignment will be examined to determine the relationship with missingness. Sensitivity analyses will be conducted that assume any person lost to follow up had constant levels of drug use based upon their most recent measurement point. This will provide some guidance as to the amount of bias possibly introduced by missing data.

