Unique to this setting is the potential to identify high risk pharmaceutical opioid users, a population that is difficult to locate and engage. Interventions using brief behavior change counseling (BBCC) have been shown to significantly improve health behaviors such as alcohol use and injury, to increase entry into drug treatment as well as to reduce costs. Evidence is promising, but limited, regarding the impact of BBCC on opioid related risk behaviors.

This prospective, multi-site, randomized trial will study the effectiveness of an intervention that combines OOPEN with BBCC for both heroin users (n=500) and pharmaceutical opioid users at elevated risk for overdose (n=500). The primary outcome is subsequent opioid overdoses, ascertained by follow up interviews conducted at 3, 6 and 12 months as well as via administrative records for up to 24 months (i.e. medical records, ambulance responses, and death certificates). Hypotheses to be investigated include that the intervention recipients will have: 1) lower rates of opioid overdose, 2) reduced drug use and overdose risk behaviors, 3) more appropriate health care utilization, and 4) lower total health care costs. We will also explore whether the intervention impacts HIV risk behaviors.

Introduction

This research proposes the first prospective, clinical trial to test the effectiveness of an intervention to prevent opioid overdoses among pharmaceutical opioid users and heroin users. Naloxone distribution programs for heroin users are widespread and descriptive studies have been conducted, but prospective, randomized studies necessary to prove effectiveness have not been conducted. To date no research has been published on how to prevent overdoses among pharmaceutical opioid users, now the largest group represented in fatal drug overdoses nationally. The intervention combines two widely used interventions for related health behaviors that have not previously been combined: 1) opioid overdose prevention, education and intervention with naloxone (OOPEN) for heroin users, and 2) brief behavior change counseling (BBCC) which has been shown to prevent future harms for a range of substances.

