- Naloxone (opioid antidote) was administered approximately once a day in Seattle by medics attending to opioid overdoses in 2011. Almost all are transported to the HMC ED.
- On August 22, 2012 the Director of the Office of National Drug Control Policy, Gil Kerlikowske, called for increased action to prevent drug overdose deaths, including wider distribution of naloxone.

Objectives

Primary Aims

The primary aims are to test whether those who receive the intervention compared to standard care have:

[figure not shown]
- 1) Lower rates of opioid non-fatal and fatal overdose
- 2) Reduce drug use, in appropriate medication use, and other overdose risk behaviors

Secondary Aims

The secondary aims are to test whether those who receive the intervention compared to standard care have:

- 3) More appropriate health care utilization (e.g. fewer emergency department visits and admissions to inpatient care)
- 4) Lower total health care costs
- 5) Determine the prevalence of HIV risk behaviors among heroin and pharmaceutical opioid users at risk for overdose and whether the intervention impacts these behaviors.

Study Design

This prospective, multi-site, randomized clinical trial will compare standard care to a novel intervention that combines OOPEN with BBCC for heroin users (n=500) and pharmaceutical opioid users at elevated risk for overdose (n=500). The study will take place at Harborview Medical Center (HMC) , University of Washington Medical Center (UWMC), and Evergreen Treatment Services. The primary outcomes are subsequent opioid overdoses, ascertained by self-report interviews at 3, 6 and 12 months after recruitment as well as via administrative records for at least 24 months and self-reported drug use and other overdose risk behaviors. Secondary outcomes include: health care utilization, direct health care costs and impact on HIV risk behaviors.

Eligibility Criteria

Inclusion for all subjects:

- 1) Meets study definition of elevated risk of future opioid overdose
 - Reason for visit is opioid overdose (regardless of frequency of use), or
 - Use of pharmaceutical opioids not prescribed to the patient 2 or more times in the prior month, or
 - Use of other opioids, alcohol, benzodiazepines or stimulants within two hours of using opioids 2 or more times in the prior month, or
 - Average daily dose of prescribed opioids consumed is greater than 10 mg morphine equivalent analgesic dose or higher for 15 or more days in the last 30.

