- Subjects will be given a study brochure that covers the information in the video and reviews the Washington State 911 Good Samaritan overdose law which provides immunity from prosecution for drug possession charges to overdose victims and bystanders who seek aid in an overdose event.
- Prescribing and dispensing overdose rescue kits including 2 doses of intra-nasal naloxone, a disposable rescue breathing mask, and disposable gloves.
- Subjects in the intervention group will be informed that they may have one replacement of the naloxone kit (2 doses) during the 12 month study period.

We expect the intervention to take 30-45 minutes on average based on our experience and that this is feasible and reasonable for subjects and interventionists.

Fidelity assessment for the BBCC will be done with the shortened Motivational Interviewing Treatment Integrity (MITI) instrument.

Schedule of and Sources Data Obtainment

MEASURES	DATA SOURCES AND TIMING					
	Interview			Administrative		
	Case Report Form	Base-line	3 & 6 mos.	12 mo.	Up to 10 yrs.	Up to 10 yrs.
PRIMARY AIMS						
Aim 1: Overdose						
Subject overdosed prior 3/6* months	X		X			
Subject overdosed Y/N & Date						X
Aim 2: Drug use and other overdose risk behaviors						
Alcohol/Drugs 3/6 month use frequency	X		X		X	
Opioid use following interruption past 3/6 months	X		X		X	
Using opioids without others present	X		X		X	
Avg. daily opioid dose- Prescribed Opioid Users	X		X		X	
Opioid substitution drug treatment prior 3/6	X		X		X	
Other drug treatment sought or used prior 3/6	X		X		X	
SECONDARY AIMS						
Aim 3: Health care utilization						

ED, Outpatient, Inpatient and Ambulance- # & Aim 4: Health care costs Hospital-based total direct health care costs			x	x
Aim 5: HIV Risk Behaviors	x	x	x	x
CO-VARIATES & POTENTIAL EFFECT MODIFIERS				
Demographics	x			
Employment, health insurance, income, housing	x	x	x	
Alcohol/Drugs ages of first use	x			
Medical status and satisfaction (WHO QOL BREF, EQ-5D- 3L)	x	x	x	
Behavior change plans and readiness	x			
Overdose lifetime history	x			
Possessed, "carried" naloxone, # of days past 3/6	x	x	x	
Overdose # witnessed events past 3/6 months	x	x	x	
Source of naloxone- Study, other	x	x	x	
Subject had naloxone administered to them, #, by Disposition of naloxone	x	x	x	x
Subject had negative/allergic reaction to naloxone	x	x	x	
FIDELITY ASSESSMENT OF BASELINE				
Overdose prevention & intervention training. Item Motivational Interviewing Treatment Integrity 3.1.1	x			

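### Overdose is the only primary outcome in the opening summary and the sample size, but the aims, Study Design and data schedule also make an open set of self-reported behaviours primary, with no multiplicity control

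*Combined protocol and SAP*

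**What the plan says.** The combined protocol and SAP describes the primary outcome in several places, and they do not agree.

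- **Opening summary (before the Introduction).** One outcome, in the singular: "The primary outcome is subsequent opioid overdoses, ascertained by follow up interviews conducted at 3, 6 and 12 months", supplemented by administrative records. Less drug use and less risk behaviour appear only in the list of hypotheses.
- **Objectives, Primary Aims.** Two aims. The second is "Reduce drug use, in appropriate medication use, and other overdose risk behaviors".
- **Study Design.** Outcomes in the plural: "The primary outcomes are subsequent opioid overdoses, ascertained by self-report interviews at 3, 6 and 12 months". After overdose by interview, the sentence continues "as well as via administrative records for at least 24 months and self-reported drug use and other overdose risk behaviors". Only utilization, costs and HIV risk behaviour are called secondary.
- **Schedule of data sources.** Six Aim 2 rows stand under the primary heading, beginning with "Alcohol/Drugs 3/6 month use frequency".
- **Sample Size Calculation.** "The study was powered to address aim 1, the impact of the intervention on non-fatal overdose". Drug use is mentioned there with services utilization, as one of the other outcomes.
- **Planned analyses.** "Aim 2 Test whether the intervention group has fewer overdose risk behaviors": logistic regression for binary measures and least squares for continuous ones, adjusted for baseline, with the 12-month value as outcome and robust standard errors for each model.

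No lead behaviour, composite, testing order, alpha split or rule for declaring primary success is given anywhere.

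**The concern.** A reader cannot tell from the plan whether a behavioural result is a primary result. Three places say that it is, and two treat overdose as the outcome on which the trial rests. If the behaviours are primary, their number is not fixed: the Study Design wording ends in an open category, and the alcohol and drug row of the schedule covers several substances. Each is tested in its own model, and nothing limits the chance that at least one is significant by luck.

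The behaviours are self-reported, and the counselling session addresses those same behaviours with intervention participants. A chance finding among them could be reported under a primary aim with less protection than the 5% level in the sample size section suggests.

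**Working it through.** **1. The plan's own figure.** Inputs from Sample Size Calculation: 20% versus 10%, level 0.05, power 0.80. Equal arms are from Randomization. Sidedness is not stated; two-sided is tried.

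- Uncorrected: n = [1.960·√(2·0.15·0.85) + 0.842·√(0.20·0.80 + 0.10·0.90)]² / 0.10² = (0.990 + 0.421)² / 0.01 ≈ 199 per arm.
- With continuity correction: (199/4)·[1 + √(1 + 4/(199·0.10))]² ≈ 219 per arm.

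The stated 219 is reproduced as one two-sided 5% test of overdose in each user group. At the planned 250 per arm, before dropout, power is 88% (85.5% with the correction). The sample size arithmetic is sound. It leaves no alpha for further primary tests.

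**2. Number of Aim 2 tests.** The schedule's six rows are: frequency of alcohol and drug use; opioid use after an interruption; using opioids with nobody else present; average daily dose (labelled for prescribed opioid users); opioid substitution treatment; other drug treatment. The analysis names one time point, 12 months, so repeated visits add no tests. Pooled over user groups there are 6 tests. Split by user group there are 12, or 11 if average daily dose is tested only in the pharmaceutical group.

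**3. Chance of at least one false positive.** The 5% level for Aim 2 is assumed, since the plan states it only for the sample size. For k independent tests the chance is 1 − 0.95^k; counting only false positives in favour of the intervention, it is 1 − 0.975^k.

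| Reading | k | Either direction | Beneficial only |
|---|---|---|---|
| Pooled | 6 | 1 − 0.735 = 26% | 1 − 0.859 = 14% |
| By user group, dose in one group | 11 | 1 − 0.569 = 43% | – |
| By user group | 12 | 1 − 0.540 = 46% | 1 − 0.738 = 26% |

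The documents give no correlations between measures. Simulation with equally correlated normal statistics (400,000 draws, two-sided) gives, for 6 tests, 24% at correlation 0.3, 21% at 0.5 and 16% at 0.7. For two independent user groups of 6 tests, 1 − (1 − 0.241)² = 42% and 1 − (1 − 0.207)² = 37% at correlations 0.3 and 0.5.

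**4. What moves the count.** Dividing the alcohol and drug row by substance raises it. Leaving out the two drug-treatment rows, which may not count as risk behaviours, lowers it: four pooled tests give 1 − 0.95⁴ = 19%.

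**5. Price of keeping everything primary.** Overdose plus six behaviours is 7 tests per user group. A Bonferroni split gives 0.05/7 = 0.00714. Overdose would then need 337 per arm (continuity-corrected), and power at 250 per arm falls to 67% (uncorrected).

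**The case against.** The strongest reply is that Aims 1 and 2 are separate hypotheses. A significant behaviour would support an Aim 2 claim, not an overdose claim, and testing Aim 2 leaves the error rate of the overdose test unchanged. Powering on Aim 1 alone also signals that overdose has priority, and the Aim 2 analysis does fix the time point, the baseline adjustment and the predictor.

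Much of this stands. The overdose test keeps its 5% level, and repeated visits do not add tests. But Aim 2 is itself labelled primary and contains several unranked measures, so the error rate for a claim under that aim is still uncontrolled. Basing the sample size on Aim 1 is not a testing order.

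A reader might go further and infer that primary success may be declared on any one of about a dozen 5% tests even if overdose is unchanged, with 46% as a floor. The documents do not support that. They contain no rule that any single test suffices. The Aim 2 paragraph does not split by user group, and the cost analysis works with 500 per arm, which is both groups together. The sample size section does treat each user type as its own study, so the split reading is possible but not established. Because some of the choices above lower the count, 46% is one value in a range, not a lower bound.

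It can also be argued that behaviours deserve primary status because the counselling targets them. That is a legitimate design choice, but it would need a lead measure or an alpha split, and the sample size does not provide for one.

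**Conclusion.** The concern holds as a conflict over what is primary, combined with uncontrolled multiplicity within Aim 2. On the pooled reading, six tests at an assumed two-sided 5% give about a 26% chance of at least one false positive if independent (24% and 21% at assumed correlations of 0.3 and 0.5), or about 14% in the beneficial direction. On the split reading, with 11 to 12 tests, it is about 43% to 46% if independent. Which reading applies is not stated.

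The exact size rests on the assumed level, the assumed correlations and the row count. The direction does not: six pooled tests at correlation 0.7 still give 16%, about three times the nominal 5%. The 219 per arm is correct for overdose and is not in question.

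**What to change.** - **Primary outcome.** Name overdose (Aim 1) as the only primary outcome for each user group in the opening summary, Primary Aims, Study Design and the data schedule. The schedule heading must change too, or the conflict remains. This matches the existing sample size, so 219 per arm stands.
- **Aim 2.** Relabel it as key secondary. In Planned analyses, give a closed list of measures: which substances count in the alcohol and drug row, whether the two treatment rows belong, to whom average daily dose applies, and whether testing is pooled or by user group.
- **Error control.** Apply Holm across that list at two-sided 5%. Testing Aim 2 only after a significant Aim 1 result is optional; it is not needed to remove the fault, and it would leave all behavioural results exploratory if overdose is null.

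The cost is wording plus a stricter first threshold for any single behaviour: 0.05 divided by the number of listed measures, for example 0.05/6 = 0.0083. Sample size and data collection do not change. Overdose would still be tested at 5% in each of two user groups, with a chance of at least one false positive of 1 − 0.95² = 9.75% if independent. The plan should say that these are two separate claims, as its sample size section implies.

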 - Enrolled in opioid substitution program (e.g. methadone or suboxone) and receiving doses.

Inclusion for heroin users:

- 2) Use of heroin through any route of administration at least 2 times in the last 30 days (or if institutionalized recently, in the most recent month they were not institutionalized) with or without other risks being present.

Inclusion for prescription-type opioid users:

- 3) Use of pharmaceutical opioids at least 2 times in the last 30 days (or if institutionalized recently, in the most recent month they were not institutionalized) with other risks being present.

Inclusion for opiate registry users:

- 4) Average daily dose of prescribed opioids consumed is 30 mg morphine equivalent analgesic dose or higher without other risks being present.

In the case of known pregnancy, subjects will not be excluded and will be offered naloxone if randomized to the intervention arm.

Exclusion criteria

- 1) Unwilling to allow further access to medical or drug treatment records.
- 2) Inability to communicate in English.
- 3) Current active suicidal ideation.
- 4) Significant cognitive or psychiatric impairment (per judgment of clinical staff)
- 5) Inability to provide adequate contact information to assist with follow-up.
- 6) Under age 18 or over age 70 at time of recruitment.
- 7) Not currently living in Washington State or planning to move from Washington State within the following year.

8) Receiving treatment for sexual assault.

9) Have non-expired take-home naloxone at home, on their person, or in their possessions.

Participation in the study is not appropriate for subjects under care for terminal illness, as known reduced life expectancy may skew study results, and the use of high doses of opioid medications may be used during end of life care.

Potential Subjects Identified

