Secondary data on health care and drug treatment utilization will be obtained from Washington State (separate IRB action pending) using the following sources:

- Treatment and Assessment Report Generation Tool (*TARGET*) for drug treatment admissions data
- The Comprehensive Hospital Abstract Reporting System (CHARS) for hospital admissions

Information on any ambulance transports will be obtained from the Seattle Fire Department's Medic 1 unit.

In the event of a subject death during the study we will request information on cause of death from the King County Medical Examiner's Office. If a subject cannot be located we will also check this source to see if they have died and if so to obtain data on the cause of death. If we are unable to locate a subject during the course of the study or at final follow-up we will utilize the King County Jail Inmate Look-up Service. At no time will subjects be contacted or study procedures attempted while the subject is incarcerated.

Intervention Description

Standard care for patients who have used opioids would vary according to individual clinical need and might include referral to drug treatment or detoxification services. Standard care would not include OOPEN and BBCC interventions as specified in this grant. After baseline data are obtained subjects assigned to the intervention undergo the following procedures:

A brief behavior change counseling (BBCC) session

- Conveys subjects' risk for overdose, based on the baseline measures
- Engages them in a reflective discussion of the pros and cons of their current patterns of use
- Has the patients identify behavior change(s) they are interested in making to improve their health
- Encourages them to share opioid overdose prevention and intervention information and materials with their family, friends, housemates, and/or drug using partners.

Education and training on opioid overdose prevention and intervention with naloxone (OOPEN)

- Subjects will view a training video on study laptops that reviews:
 - Information on risk factors for overdose and how to prevent and reduce the risk of overdose

- How to recognize an opioid overdose
- The importance of calling 911
- How to intervene in an overdose
 - Positioning a victim in rescue position
 - Brief overview of rescue breathing
 - Training on how and when to administer naloxone

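### The residence exclusion looks one year ahead, but the pharmaceutical opioid stratum is powered on two years of Washington and local records; the cost is small and cheap to reduce

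*Combined protocol and SAP*

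**What the plan says.** Exclusion criteria, item 7, excludes anyone "Not currently living in Washington State or planning to move from Washington State within the following year". The criterion is the same for both opioid-user strata.

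The Sample Size Calculation uses different windows for the two strata: "The power estimates above therefore address one year overdose rates for heroin and 2 years for pharmaceutical opioid users". For the pharmaceutical group it assumes "20% over two years which is the amount of time over which follow up via administrative data will be collected".

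Follow-up Visits schedules telephone interviews at 3, 6 and 12 months and none later. Planned analyses, Aim 1, takes self-report to 12 months and administrative data to at least 24 months. On those data, Secondary Data Sources says: "Secondary data on health care and drug treatment utilization will be obtained from Washington State". It also names the Seattle Fire Department for ambulance transports and the King County Medical Examiner for deaths. Other analyses refers to records of the two study hospitals and King County ambulance data.

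The first Aim 1 analysis is an unadjusted logistic regression on the probability of overdose, followed by a Cox model for time to overdose. For utilization, under Aims 3 and 4, the plan allows rate models "with an exposure adjustment should there be a need to account for differing amounts of follow-up time". Aim 1 has no matching provision.

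**The concern.** The residence screen covers half of the period on which the pharmaceutical stratum is powered. Someone who says at screening that they will leave Washington in 15 months is eligible. A non-fatal overdose after that move would not appear in any named source, and no interview is scheduled that could report it.

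The plan does not say that such a person is counted as overdose-free. That is what happens by default when a yes/no outcome is built from records that cannot see the subject and no rule ends their follow-up. If it happens equally in both arms, both observed two-year rates fall, the absolute difference shrinks and power is lost. If it happens unequally, the comparison itself is biased.

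**Working it through.** **Inputs from the plan (Sample Size Calculation).** Rates 20% versus 10%; alpha 0.05, sidedness not stated; power 0.80; 219 per arm needed, 250 per arm enrolled. For pharmaceutical users: "We are assuming an annual overdose rate of 10% for pharmaceutical opioid users, or 20% over two years".

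**Assumptions, not in the documents.** A share f of all subjects leaves Washington in year 2. Leavers lose a share m of their two-year events: m = 0.50 if all go at the start of year 2, and m = 0.25 if they go evenly through it. There is no other loss to follow-up.

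**Step 1: reproduce 219.** Two-sided test, d = 0.10, mean rate 0.15:

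- Uncorrected: n = [1.960 × √(2 × 0.15 × 0.85) + 0.842 × √(0.16 + 0.09)]² / 0.10² = (0.990 + 0.421)² / 0.01 ≈ 199.
- Continuity-corrected: n' = (n/4) × [1 + √(1 + 4/(n × d))]² = 218.5, which rounds up to 219.

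The corrected two-sided formula matches the plan exactly. The uncorrected two-sided (199) and one-sided (157, or 177 corrected) versions do not. Solving the same corrected formula for power gives 0.801 at 219 per arm and 0.855 at 250.

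**Step 2: count leavers as non-events, equally in both arms.** Observed rates become 0.20 × (1 − f × m) and 0.10 × (1 − f × m). For f = 10% and m = 0.50 the factor is 0.95, giving 19.0% versus 9.5%.

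| Share leaving in year 2 | When | Observed rates | n needed per arm | Power at 250 | Power at 219 |
|---|---|---|---|---|---|
| 0% | – | 20.0% vs 10.0% | 219 | 0.855 | 0.801 |
| 5% | start | 19.5% vs 9.75% | 226 | 0.843 | 0.788 |
| 10% | evenly | 19.5% vs 9.75% | 226 | 0.843 | 0.788 |
| 10% | start | 19.0% vs 9.5% | 232 | 0.831 | 0.775 |
| 20% | start | 18.0% vs 9.0% | 247 | 0.805 | 0.746 |
| 30% | start | 17.0% vs 8.5% | 264 | 0.777 | 0.715 |

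At 250 per arm, power drops below 0.80 only near 30% leaving at the start of year 2. At 219 evaluable per arm there is no slack, so any such loss takes power below 0.80.

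**Step 3: effect measures under equal leaving.** The risk ratio stays at 0.50. The odds ratio, which the logistic model estimates, is (0.10/0.90)/(0.20/0.80) = 0.444 with no leaving and (0.095/0.905)/(0.19/0.81) = 0.448 with 10% leaving at the start of year 2.

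**Step 4: unequal leaving.** If the true rate were 20% in both arms and 10% of one arm only left at the start of year 2, the plan would observe 0.20 × (1 − 0.10 × 0.50) = 19% versus 20%. That one-point gap is produced by residence alone.

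**Step 5: does any planned safeguard reach year 2?** The completeness check in Other analyses relies on interview questions, so it stops at month 12. The sensitivity analysis in Missing data and dropouts carries forward drug use, not overdose status. The exposure adjustment is stated for utilization only. The Cox model could censor leavers, but no censoring rule is given and nothing dates a move after month 12.

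**The case against.** The strongest reply is that these figures do not belong to item 7. The exclusion can screen out only people who already plan, at screening, to leave during months 13 to 24. The 5% and 10% cover every leaver, and the documents give a rate for neither group. If only 1% to 2% hold such a plan (an assumption), the same corrected formula with departure at the start of year 2 gives power of 0.852 to 0.850 at 250 per arm, against 0.855. This stands: rewording item 7 alone achieves little.

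The enrolment of 250 rather than 219 is also meant partly to absorb loss to follow-up. That stands too, although the same margin must cover every other loss.

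A reader might infer that the plan ignores moves altogether. It does not. The schedule of measures collects housing at follow-up, and Other analyses asks about services outside the study hospitals and the King County ambulance area, with a comparison by arm. Interviews are by phone, so a subject who moves can still report overdoses up to month 12. The Summary also lists death certificates without a geographic limit, so some out-of-state deaths might be found. What remains uncovered is non-fatal overdose after a move in months 13 to 24.

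A reader might also infer that item 7 was deliberately set to match the interview period, or that the two-year result is biased in a known direction. The plan states no rationale for item 7, and nothing in it suggests that the arms would leave at different rates.

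**Conclusion.** The mismatch between a one-year residence screen and a two-year powered outcome is explicit, and no stated analysis rule handles time out of state. The consequence is minor: power at 250 per arm goes from 0.855 to between 0.843 and 0.831 for 5% to 10% leaving at the start of year 2, with a negligible shift in the relative effect when leaving is equal. Those figures rest on assumed leaving shares, on the plan's 10% annual rate and 50% reduction, and on no other losses.

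The documents do not support the stronger reading that the trial is materially underpowered or its estimate distorted for this reason. Bias requires unequal leaving, which is possible but not shown; the difficulty is that the plan could not detect it after month 12. This is a cheap improvement, not a flaw that threatens the trial. The heroin stratum is powered on one year, so its power basis is unaffected, although any 24-month analysis of that group has the same gap.

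**What to change.** 1. Extend item 7 to a two-year horizon for pharmaceutical opioid users.
2. At the existing 3, 6 and 12-month calls, add state of residence, date of any move and any planned move date to the housing and out-of-area service questions already asked.
3. In the 24-month Cox analysis, censor at a known move out of Washington, and report known moves by arm.
4. Keep the intent-to-treat logistic comparison on all randomised subjects. Dropping known leavers selects on post-randomisation information, so do it only as a labelled sensitivity analysis.
5. State as a limitation that unplanned moves after month 12, and moves within Washington but outside King County, remain only partly observable.

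The cost is one changed phrase at screening, a few items in calls already scheduled, and one censoring rule. The downside is that a few otherwise eligible subjects are excluded. For anyone already enrolled, items 2 to 5 can still be applied.
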